The assessment battery takes 15 minutes to complete on average based on the use of a similar question battery with an adolescent population in other studies. Each young person will be supported during completion, at baseline by staff in the services and at 6- and 12-month by researchers who will be blind to participant allocation. Research staff will provide training in baseline data collection to staff in Bridgend across the five services through an interactive in-person training session and this will include a training manual and on-going support. At the end of each assessment point and at the end of any qualitative interview the young person will be provided with an opportunity to debrief and reflect on the impact of answering the questions. This debrief is designed to identify any negative impacts of reflecting on themselves and any potential re-traumatisation. If issues are identified, the potential adverse event standard operating procedure will be activated, and trauma leads in each service asked to conduct an assessment and provide any necessary intervention. All adverse events in both arms of the study will be recorded and reported.

In addition to key demographics (age, sex, ethnicity, and IMD) that will be assessed at baseline we will assess the exposure to adverse child experiences assessed on entry to the service using existing records.

Six months after randomisation, in both arms of the study, young people will be contacted by phone or email by researchers and asked to complete the short revised therapeutic alliance scale for children (TASC-r; (Shirk and Saiz, 1992)), this assesses the quality of the relationship between the young person and staff member. Therapeutic alliance is a strong predictor of outcome, and this will be used in the prognostic model (objective 5).

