Secondary outcomes will be assessed in a similar way by establishing diagnostic plots to identify the most appropriate regression approach; logistic for dichotomous outcomes, ordinal for ordered categorical outcomes, linear for continuous outcomes and fractional for proportions. Stratification factors and baseline covariates will be included within the model.

If the missing data exceeds 5%, sensitivity analyses will be performed using a pattern mixture approach and multiple imputation to compare the sensitivity of conclusions to varying assumptions about the missing data, particularly whether data is missing at random (MAR) or missing not at random (MNAR). This allows for an assessment of both random and systemic bias. Results based on complete data analysis, MAR and MNAR will be presented to explore the influence of missing data on outcomes observed.

We will conduct a Complier Average Causal Effects (CACE) analysis using an instrumental variable framework to explore the impact of compliance on the primary outcomes at different levels of compliance, both fidelity to the steps involved in each tier and quintiles of compliance. CACE weights the analysis by the ITT treatment effect by the proportion of compliance, this allows the estimation of unbiased treatment effects and maintains the allocation in the analysis.

Objective 3: For staff we will explore the differences between the groups in terms of overall wellbeing, perceptions of working in a trauma informed manner and confidence in working with young people who have experienced adverse childhood experiences derived from the SWEMWBS and ARTIC questionnaire at months 6 and 12 using linear regression adjusted for baseline score and service. Staff turnover and proportion absence will be assessed in a similar manner using fractional regression.

Objective 5: Stepwise regression analysis will be performed to model the relationship between pre-randomisation factors and demographics, on observed outcomes at 6 months.

Interaction terms with allocation arm will be included in the analysis, and a significance level of 0.1 will be used to determine which factors are to be included in the regression model. Pre-randomisation factors will include sex, age, ethnicity, IMD, family cohesion, adverse childhood experiences assessed by the service, and process measures, staff perceptions, staff confidence, and therapeutic alliance. The allocated arm will be included in this analysis as an interaction term.

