The efficacy trial design is a mixed method, two level, individually randomised controlled trial of a trauma informed intervention, Trauma Recovery Model Relationship Building Together (RBT), versus business as usual (BAU) for adolescents and young adults served by Bridgend Youth Services (youth justice, edge of care, youth development and early help). There are two levels to the study randomisation. Level one involves selecting staff to be trained in RBT. This allocation is done for all staff, after baseline staff data collection, and is conducted by an on-line independent secure randomisation service, Sealed Envelope Ltd. Consent will be sought from all eligible staff prior to randomisation. As allocations are done at the same time and because we want to maximise balance across the groups on key parameters, we will employ minimisation for the allocation of staff. Our aim will be to maximise balance in terms of service (youth justice, edge of care, children's services, youth development, and early help) and speciality (specialised staff versus generic staff). Provision has been made to conduct a second wave of staff randomisation and TRM training if there is a high turnover of staff throughout the trial – a high turnover is one that exceeds 30%.

Level two allocation involves the randomisation of young people to RBT or BAU. This will be conducted by research staff, using a secure, on-line randomisation service (Sealed Envelope Ltd). after informed consent has been taken and the baseline assessment completed and before any trauma screening has been conducted. The allocation will involve an equal probability of receiving RBT or BAU and will employ random permuted blocks of variable size (4, 6 or 8) with a random block seeded throughout. Randomisation will be stratified by service (youth justice, edge of care, children's services, youth development and early help), sex (male, female), and age group (<15 years, 15 years or more). Stratification variables have been chosen to ensure allocation is balanced across services, sex, and age as some workers specialise in working with older or younger males and females.

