We have used an effect size difference of 0.25 as an important difference; this equates to a difference in volume of offences of circa 12% over a 6-month period, similar effects as found in other psychologically focussed interventions to reduce recidivism in adolescent populations (Hodgkinson et al., 2021). To detect this difference or greater, using a two-sided test, alpha of 0.05 and power at 80% requires 506 young people to be followed-up at our primary endpoint, 6-months post-randomisation, 253 in each group. There is no reliable literature on pre- and post-test correlations for the SRDS, so we have erred on the side of caution and not accounted for this in the sample size calculation as an incorrect assumption increases the risk of an under-powered trial. If we take a potential loss to follow-up of 10%, similar to attrition found in our other studies of young people (Coulton S et al., 2023) this inflates the required baseline sample to 562. We have 73 potential interventionists, 35 randomised to control and 36 randomised to be trained in the intervention delivery. Each interventionist can manage a harmonic mean of 10 young people through the course of the study. To achieve our target, we would need to have at least 56 of these interventionists participating throughout the trial, 28 in each arm, thus allowing for a potential loss of interventionists of 17, 23% of those available.

Assuming only 80% of young people approached consent to take part as found in similar studies (Coulton S et al., 2023) means we would need to approach 702 young people, over the recruitment period. Allowing for a slower start of 20/ per month recruited over the first three months, means 36 will need to be recruited in each month between January 2024 and February 2025, allowing for a six-month follow-up for the interim report submitted in September 2025.

Analysis

All analysis is conducted using STATA 16 SE. Analysis will be conducted and presented in accordance with the CONSORT guidelines. The validity of randomisation will be explored by presenting baseline measures of central tendency and estimates of precision for continuous variables, and proportions for categorical variables broken down by allocated arm and stratification factors for both staff and participant samples.

Primary outcome analysis

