$$SRDS12_{i,j} = \alpha + \beta_1(\text{allocation})_{i,j} + \beta_2(SRDS0)_{i,j} + \beta_3(\text{sex})_{i,j} + \beta_4(\text{age})_{i,j} + \beta_5(\text{service})_j + \varepsilon_i$$

Where for participant i within service j ; $SRDS12$ is the 12-month SRDS score, $allocation$ is the allocated group, $SRDS0$ is the baseline SRDS score, sex is the participant sex, age the age group, $service$ the service level dummy variables to adjust for fixed effects and ε_i the individual level error.

Other secondary outcome analysis at months 6 and 12, will be based on the ITT dataset. All secondary outcomes are continuous in nature, and after the examination of diagnostic plots to establish that the underlying assumptions for a linear analysis of covariance are met, they will be using an approach similar to that used in the primary outcome analysis (eq.3).

$$OUT_{i,j} = \alpha + \beta_1(\text{allocation})_{i,j} + \beta_2(OUT0)_{i,j} + \beta_3(\text{sex})_{i,j} + \beta_4(\text{age})_{i,j} + \beta_5(\text{service})_j + \varepsilon_i$$

Where for participant i within service j ; OUT is the 6 or 12-month outcome, $allocation$ is the allocated group, $OUT0$ is the baseline outcome value, sex is the participant sex, age the age group, $service$ the service level dummy variables to adjust for fixed effects and ε_i the individual level error.

Staff outcomes (ARTIC score, wellbeing and rates of absence) will be analysed using an analysis of covariance adjusted for baseline values and stratification factors: service and specialist versus generic.

Outcomes will be presented for each allocated group as means and the associated estimates of precision, 95% confidence intervals.

Subgroup analyses

To maintain power in the analysis we will avoid analysing sub-groups and instead use the whole sample for latent class analysis to explore for the emergence of clusters of participants who may have a differential response to the RBT intervention. Latent class approaches allow for clusters to emerge from the data rather than being pre-specified. In addition to the baseline variables being collected we will also include measures of ethnicity, material deprivation and therapeutic alliance assessed at month 6 using the short revised therapeutic alliance scale for children (TASC-r; (Shirk and Saiz, 1992)).

Further analyses

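### Month-6 therapeutic alliance, which RBT aims to change, is an indicator in the latent class analysis for differential response, so arm contrasts within classes may not be randomised comparisons

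*SAP*

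**What the plan says.** **Objective 6.** The SAP (Subgroup analyses) runs a whole-sample latent class analysis to find clusters that may respond differently to RBT. Its inputs are the baseline variables, with ethnicity, deprivation and "therapeutic alliance assessed at month 6 using the short revised therapeutic alliance scale for children" added. It states no restriction to variables measured before randomisation.

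**Timing.** The Protocol (Secondary outcomes) describes the alliance collection: "Six months after randomisation, in both arms of the study, young people will be contacted by phone or email by researchers". The assessment schedules in both documents list it under process measures, with a month-6 tick and no baseline value.

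**Objective 5.** The documents differ.
- The Protocol (Analysis, Objective 5) gives a list introduced as pre-randomisation factors that ends with "adverse childhood experiences assessed by the service, and process measures, staff perceptions, staff confidence, and therapeutic alliance", and allocated arm enters as an interaction. The Protocol's Study objectives (item 5) and Secondary outcomes also assign alliance to this prognostic model.
- The SAP (Further analyses) leaves alliance out of its pre-randomisation list and uses it as a process measure in an additional model restricted to the RBT arm.
- The Protocol's own later list (Implementation and process evaluation, Research Methods) also omits it.

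**The concern.** A variable can define subgroups for a randomised comparison only if allocation cannot affect it. Alliance does not meet that condition on the trial's own premises. The Protocol (Study rationale and background) makes building relationships with young people an aim of the model and trusting relationships a key component. Its Secondary outcomes section calls alliance a strong predictor of outcome.

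If RBT lifts alliance, some RBT participants reach a high-alliance class who would not have reached it under BAU, so the two arms within that class started from different places. There is a second route. The month-6 SRDS looks back over the six months that end when alliance is rated, so offending in that window may itself have changed the relationship.

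What is at stake is the trial's account of who benefits. Both documents avoid conventional subgroup analysis, so the latent classes are a main route to such statements, and the Protocol intends to say for whom the intervention works.

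**Working it through.** **1. Scale.** The plan has no figure on this point, so its sample size serves only to fix the scale. The SAP states: "We have used an effect size difference of 0.25 as an important difference", and "using a two-sided test, alpha of 0.05 and power at 80% requires 506 young people to be followed-up". The normal approximation gives 2 × (1.960 + 0.842)² / 0.25² = 251.2, so 252 per arm. The exact t calculation gives 253, as stated, and 506 / 0.90 = 562.2, stated as 562. The plan's figure is reproduced, and 0.25 SD is the benchmark below.

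**2. Inputs that must be assumed.** The documents give neither the effect of RBT on alliance (a, in SD) nor the strength of the alliance–offending correlation (r). Both are varied over 0.3 to 0.5.

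**3. Extreme case: classes split at the median of alliance alone.** Suppose RBT has no effect on offending, and alliance and offending are linked only through prior engagement. With 1:1 allocation, the overall median lies a/2 above the BAU mean. The high-alliance class then holds Φ(a/2) of RBT and Φ(−a/2) of BAU. In both classes the spurious RBT minus BAU difference in offending is

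r × φ(a/2) × [1/Φ(−a/2) − 1/Φ(a/2)].

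For a = 0.3 the factor after r is 0.3945 × (2.271 − 1.787) = 0.191. For a = 0.5 it is 0.3867 × (2.492 − 1.670) = 0.318.

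| a | r | Share in high class, RBT v BAU | Spurious difference (SD) |
|---|---|---|---|
| 0.3 | 0.3 | 56% v 44% | 0.06 |
| 0.3 | 0.5 | 56% v 44% | 0.10 |
| 0.5 | 0.3 | 60% v 40% | 0.10 |
| 0.5 | 0.5 | 60% v 40% | 0.16 |

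The sign is towards more offending under RBT, so a real benefit would look smaller. The expression is identical in the high and low classes, so the difference between classes is zero.

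**4. Closer to the plan: a two-class model on several indicators.**
- With one alliance score beside several baseline indicators, the within-class shift was about 0 to 0.05 SD. It was near 0.01 SD or less when the baseline indicators separated the classes well.
- With five weak baseline indicators and three alliance items, a = 0.5 and a true effect of −0.25 SD in everyone, class-specific effects were −0.16 and −0.15, and the high-alliance class held 64% of RBT v 44% of BAU. With the baseline indicators alone, the effects were −0.27 and −0.25, and membership was 50% in each arm.

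**5. When there is no bias.** If neither RBT nor offending during follow-up moves alliance, within-class effects stay at −0.25. If only offending moves it (a = 0, split on alliance), they lie between −0.20 and −0.24. If both act (a = 0.3 to 0.5, split on alliance), they run from −0.01 to −0.20. The table in step 3 is therefore an illustration and not a bound.

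**6. Interaction test.** With 506 participants and the same true effect in everyone, a class-by-arm interaction reached p < 0.1 in 9% to 12% of simulated trials, close to the nominal 10%. With a top-quarter split on alliance (a = 0.5, alliance correlated 0.5 with an unmeasured offending propensity), the class-specific effects were −0.14 and −0.18. Both are attenuated and they differ only modestly.

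**The case against.** The strongest reply has four parts.

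- **Objective 5 is already handled.** The Protocol defers to the SAP for the analysis. The SAP keeps alliance out of the pre-randomisation list, and its RBT-arm-only model has no arm contrast to bias. This stands. A reader might infer that the trial will analyse alliance as a baseline effect modifier, but only the Protocol's objective 5 wording suggests it, and the SAP and the Protocol's own Research Methods list contradict that wording. What remains is a conflict to reconcile.
- **The larger figures come from a split on alliance alone.** The SAP plans a model on many variables. This also stands: 0.06 to 0.16 SD, which is 24% to 64% of the 0.25 target, should not be read as this plan's bias.
- **No false interaction is shown.** A reader might infer that the plan will manufacture differential response. The calculations do not support that. They show a similar shift in each class. Class-specific effects are still what a report on who benefits would be likely to present.
- **The analysis is exploratory.** No class-by-arm estimator is written down, so contrasts within classes are inferred from the stated purpose. That lowers the weight of the point but does not remove it.

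It is also tempting to say that attrition decides class membership, because those lost at month 6 have no alliance score. That goes too far: a latent class model can be fitted with a partly observed indicator.

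**Conclusion.** The point holds for objective 6. A post-randomisation measure of something RBT sets out to change is a class indicator in an analysis of differential response, so class membership can follow from allocation or from offending. Whether this produces bias depends on RBT or offending actually moving alliance. The trial's theory expects the first, but the documents do not quantify it. On the assumed values, class-specific effects shift by about 0 to 0.05 SD with one alliance score among several baseline indicators, and by 0.06 to 0.16 SD if alliance alone forms the classes. For objective 5 the finding is a wording conflict within the Protocol and between the Protocol and the SAP. The primary ITT analysis and the sample size are untouched, so this is an inexpensive improvement and not a threat to the main result.

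**What to change.** 1. **SAP, Subgroup analyses:** form the latent classes from pre-randomisation variables only, including ethnicity and deprivation, and then examine class by allocation. Remove TASC-r from the indicators.
2. **Use of TASC-r:** keep it as a mediator or process variable, in the mediation work described in the Protocol (Research Methods) and in the SAP's RBT-arm-only model.
3. **Protocol, Study objectives (item 5), Secondary outcomes, and Analysis (Objective 5):** take alliance and the other process measures out of the prognostic or pre-randomisation factors with arm interactions, to match the SAP and the Research Methods list. Baseline ARTIC may stay.
4. **Mediation outcome:** if month-12 SRDS is used, apply the six-month recall given under the Protocol's Primary outcome heading. Reconcile this with the twelve-month recall in the summary tables of both documents. With twelve-month recall, half the window would come before the month-6 alliance rating.

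The cost is wording in both documents, plus a short specification of the mediation model, which the SAP currently lacks. No data are lost, and the sample size and assessment schedule do not change.

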## Impact evaluation

### Study objectives

1. To conduct a prospective RCT to evaluate the efficacy of the Relationship Building Together (RBT) approach compared with business as usual (BAU) on offending behaviour, measured using the Self Report Delinquency Scale (SRDS), over 6- and 12-months post-randomisation, in a population of young people, aged 10-21 years inclusive, accessing services provided by Bridgend Youth Offending Team, Bridgend Youth Development Services, Bridgend Early Help Hubs, Bridgend Edge of Care Services, and Bridgend Children's Services.
2. To evaluate the efficacy of the RBT versus BAU in terms of emotional regulation, peer, prosocial, conduct, hyperactivity, internalising and externalising behaviours (SDQ), wellbeing (SWEMWBS), psychological health (GHQ12), family cohesion (BFRS), school, work, and criminal justice involvement (CSRI), in a population of young people, aged 10-21 years inclusive, accessing services provided by Bridgend Youth Offending Team, Bridgend Youth Development Services, Bridgend Early Help Hubs, Bridgend Edge of Care Services, and Bridgend Children's Services, at 6- and 12-months post randomisation.
3. To evaluate the impact of RBT versus BAU on staff perception of trauma informed care (ARTIC), staff wellbeing (SWEMWBS), staff turnover and staff absence in the 6 and 12 months after training across Bridgend Youth Offending Team, Bridgend Youth Development Services, Bridgend Early Help Hubs, Bridgend Edge of Care Services, and Bridgend Children's Services.
4. To conduct a micro-costing exercise to provide estimates of the cost of delivering the intervention from the perspective of the intervention delivery organisation.
5. To develop a prognostic model exploring the baseline demographics (age, sex, ethnicity, IMD), psychological (SDQ, GHQ12, ACES), therapeutic alliance (TASC-r) and family factors (BFRS) that may impact observed outcomes and using the results to elaborate mechanisms of change and where appropriate revise the intervention logic model.
6. To conduct a latent class analysis to explore potential interactions between population subgroups, intervention received, and outcomes observed.

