Objective 6: To maintain power in analysis we will avoid the analysis of sub-groups. We will use latent class analysis to explore the existence of subgroups within the sample who may have a differential response to the intervention.

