In addition to quantitatively understanding the mechanism of action, the qualitative analysis will provide an opportunity to explore the perceptions of the intervention from the point of view of a variety of stakeholders. The analysis will allow us to explore what elements of the interventions are useful and what elements are unnecessary, issues around how the interventions are planned and implemented and the perceived barriers or facilitators of implementation in usual practice.

Through a detailed exploration of the key dimensions, we plan on stating our logic model at the start of the project and revise this again at the end of the efficacy stage. The logic model will incorporate the qualitative research exploring stakeholder perceptions of acceptability and usefulness, hindrances and facilitators associated with the process and intervention but will also combine quantitative analysis exploring adherence, dosage, fidelity, and mediators associated with behaviour change. This mixed methods synthesis will enable us to understand what works, how it works, when it works and for whom it works and provide a detailed elaboration of the mechanisms and processes through which it works.

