To explore the proposed mechanism of change we will conduct a prognostic linear regression analysis to model the relationship between pre-randomisation factors; age, gender, ethnicity, IMD, SRDS, SDQ, BFRS, GHQ and observed outcomes at 6- and 12- months respectively on the primary outcome at either 6- or 12-months. Interaction terms with allocation arm will be included in the analysis, and a significance level of 0.1 will be used to determine which factors are to be included in the regression model. This analysis will be augmented by an additional

analysis including participants in the RBT arm only using the same pre-randomisation factors but also including process measures of compliance, therapeutic alliance, and interventionist attitude to trauma informed practice.

Interim analyses and stopping rules

No interim analyses are planned. The trial will only be stopped if evidence emerges of a serious adverse event associated with participation in the trial. As the intervention has already been implemented in practice with youth offending populations there is no evidence at the outset that a serious adverse event is likely to occur.

Longitudinal follow-up analyses

Assessments are conducted at baseline, prior to randomisation and then again at months 6 and 12, with 6-months being considered the primary endpoint. Table 2 provides an overview of what measures are being conducted at each time-point.

Outcome	No of items	Baseline	Six months	Twelve months
Primary				
Self-reported delinquency (SRDS) ¹	36	✓	✓	✓
Secondary				
Strength and Difficulties (SDQ) ¹	25	✓	✓	✓
Wellbeing (SWEBWMS)	7	✓	✓	✓
Psychological Distress (GHQ12)	12	✓	✓	✓
Family environment (BFRQ)	16	✓	✓	✓
Receipt Inventory (CSRI)	8	✓	✓	✓
Staff attitudes to trauma informed care (ARTIC)	35	✓	✓	✓
Staff wellbeing (SWEBWMS)	7	✓	✓	✓
Staff turnover & absence	2	✓	✓	✓
Exploratory				
Adverse childhood experiences (ACE-Q)	10	✓		
Process				
Therapeutic relationship	12		✓	
Proportion of sessions planned & delivered	1		✓	✓

Imbalance at baseline

Rather than just assume the randomisation has worked, we will assess observed balance by comparing the means and distributions of the groups created by randomisation for both participants and staff. If they are systematically different across those variables we observe – e.g. always larger / smaller in one group - then that would suggest the randomisation has not been successfully implemented. Baseline equivalence following randomisation will be

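### The objective 5 model selects factors at p<0.1 with no safeguard; if the rule also screens the interactions with arm, it names a false effect modifier in about 57% of trials that have none

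*SAP*

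**What the plan says.** The SAP, under Further analyses, describes a prognostic linear regression of the primary outcome at 6 or 12 months. The baseline candidates are the eight that open this list: "age, gender, ethnicity, IMD, SRDS, SDQ, BFRS, GHQ and observed outcomes at 6- and 12- months". It continues, "Interaction terms with allocation arm will be included in the analysis", and the same sentence adds that "a significance level of 0.1 will be used to determine which factors are to be included in the regression model".

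The protocol (Analysis, objective 5) applies the same 0.1 level but names the procedure: "Stepwise regression analysis will be performed to model the relationship between pre-randomisation factors and demographics, on observed outcomes at 6 months". Allocated arm enters as an interaction term.

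The candidate lists differ:

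- SAP, Further analyses: eight factors.
- Protocol, Study objectives, objective 5: nine. To age, sex, ethnicity and IMD it adds "psychological (SDQ, GHQ12, ACES), therapeutic alliance (TASC-r) and family factors (BFRS) that may impact observed outcomes".
- Protocol, Analysis, objective 5: nine. "Pre-randomisation factors will include sex, age, ethnicity, IMD, family cohesion, adverse childhood experiences assessed by the service, and process measures", the last being staff perceptions, staff confidence and therapeutic alliance.
- Protocol, Research Methods (process evaluation): six, again with interactions with arm and the 0.1 level.

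Objective 5 says that the results will help to explain mechanisms of change and, where appropriate, lead to revision of the logic model. For objective 6 the protocol says "To maintain power in analysis we will avoid the analysis of sub-groups". The SAP repeats this under Subgroup analyses.

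**The concern.** A factor-by-arm interaction tests whether the treatment effect differs across levels of that factor. Screening a list of them at 0.1 is therefore a set of subgroup tests, in a plan that says it avoids subgroup analysis for the sake of power. With several tests at a liberal level, some term is likely to pass by chance. The data that selected the term then supply its coefficient, p-value and confidence interval, so the estimate is pushed away from zero and the interval undercovers.

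Neither document gives a multiplicity adjustment, shrinkage, validation or a warning about post-selection inference for this model. A reader could take a retained interaction at face value. A false modifier could then enter the account of how the intervention works, while a real but modest one that missed the cut would go unreported.

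**Working it through.** **Plan's own figure.** The documents state no error rate for the screen. The sample size used below does reproduce. For an effect of 0.25 SD, two-sided alpha 0.05 and 80% power, 2 x (1.960 + 0.842)^2 / 0.25^2 = 251.2, so 252 per arm by the normal approximation. The noncentral t gives 253 (power 80.1%), as stated. 506 / 0.9 = 562.2, against the stated 562.

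**Inputs.** The level is 0.1 per test (SAP; two-sided assumed). There are 8 interactions (SAP), or 9 or 6 (protocol lists), each counted as one term. Follow-up is 506 with 1:1 allocation. No true modifier is assumed.

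**Chance of at least one false modifier, independent tests:** 1 - (1 - 0.1)^k.

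| k | Source | Result |
|---|---|---|
| 8 | SAP, Further analyses | 1 - 0.4305 = 57.0% |
| 6 | Protocol, Research Methods | 1 - 0.5314 = 46.9% |
| 9 | Protocol, Study objectives and Analysis | 1 - 0.3874 = 61.3% |

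The expected number of false interactions with eight tests is 8 x 0.1 = 0.8.

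**Simulation, eight interactions, n = 506, 3,000 null trials per setting.** Correlations, prevalences and outcome shape are assumptions, not document figures.

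- Backward elimination at 0.1 with main effects kept, eight normal factors, common correlation 0 / 0.3 / 0.5: at least one interaction retained in 58.3% / 58.0% / 59.1%.
- All eight tested in one model, mixed binary and continuous factors, correlation 0 to 0.7 among SRDS, SDQ, BFRS and GHQ: 55% to 57%.
- Interactions tested one at a time, same settings: 51% to 57%.
- Skewed count outcome (negative binomial) fitted by linear regression: about 59%.

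The range for eight tests is thus about 51% to 59%.

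**Intervals after selection.** For a single null test, a 95% interval covers zero when p > 0.05. Given retention at p < 0.1, coverage is (0.10 - 0.05) / 0.10 = 50%. The backward-elimination runs gave 50%, 43% and 37% at correlations 0, 0.3 and 0.5, so roughly 40% to 50% against a nominal 95%.

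**The case against.** The strongest reply is that this is exploratory work. The SAP introduces it as exploration under Further analyses, and it leaves the primary estimate, alpha and interval alone. A liberal inclusion level is common in exploratory modelling, and 0.1 is a selection threshold, not a confirmatory error rate. That stands, and it limits the weight of the point. It does not remove it: neither document calls retained interactions hypothesis-generating or warns that their intervals are unreliable after selection.

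The text is also ambiguous. It applies 0.1 to factors and says that interactions will be included, so the level could be meant for main effects only. Screening of the interactions is the natural reading, not a stated one.

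Several stronger readings are tempting but unsupported:

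- *The logic model will be revised on whatever survives.* Objective 5 says only where appropriate, and Research Methods adds qualitative, adherence, dosage, fidelity and mediator evidence.
- *This model is claimed to show for whom the intervention works.* The protocol credits the mixed-methods synthesis with helping it "understand what works, how it works, when it works and for whom it works".
- *The rate always rests on at least eight tests.* One protocol list has six.
- *Using both time points takes the rate to about 81%.* 1 - 0.9^16 = 81.5% treats the 6- and 12-month tests as independent, although they use the same participants and measure.

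A strict remedy would also have a price. Assume one true continuous modifier changing the effect by 0.25 SD per SD. The standard error of the interaction is 2 / sqrt(506) = 0.089, so 0.25 / 0.089 = 2.81 and the power of a single test at 0.1 is about 88%. An eight-degree-of-freedom joint test at 5% has about 46%. A mandatory joint gate followed by Holm adjustment is therefore hard to justify for exploratory work.

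**Conclusion.** The concern holds as a defect in how objective 5 will select and report effect modifiers. If the 0.1 rule screens the interactions, more than half of trials with no true modifier would name one under the SAP's list: about 57%, with a plausible range of 51% to 59%. With the protocol's lists it is about 47% (six factors) or 61% (nine). Intervals for retained terms would cover zero about 40% to 50% of the time. These figures assume two-sided tests and one term per factor; the ranges also rest on the assumed correlations and outcome shapes. If the rule was meant for main effects only, they do not apply, but the documents would need to say so. The findings may inform the logic-model revision; nothing makes that revision automatic. The primary analysis is untouched, so this should be corrected but does not threaten the main result.

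**What to change.** In the SAP (Further analyses) and the protocol (Analysis, objective 5, and Research Methods):

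1. Delete stepwise selection and the 0.1 rule.
2. Settle one pre-specified list of baseline factors, identical in every section. Therapeutic alliance is measured at six months, so it is not a baseline factor.
3. Fit one model with all listed factors and all their interactions with arm, without selection.
4. Report every interaction with its 95% confidence interval, significant or not, and show how many were tested.
5. State that individual interactions are hypothesis-generating, at both 6 and 12 months.

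A joint test of all interactions can be reported as context, but need not be a gate and need not be followed by Holm adjustment.

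The cost is a change of wording in both documents, a longer results table and fewer modifiers named. No new data are needed.
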